14.5 Role and responsibility of the Data and Safety Monitoring Board

The PHOXSTAT DSMB is a distinct and separate entity and functions independently from the sponsor, and the Trial Office. It will be comprised of the following:

- a) [name] (chairman)
- b) [name] (statistician)
- c) [name] (methodologist)

The DSMB has the authority to stop the research in progress, remove individual subjects from the research, and take whatever steps are necessary to protect the safety and wellbeing of the subjects until the IRB can assess its reports.

In addition to reviewing individual reports forwarded by the Independent Medical Monitor, the DSMB will, in conjunction with the trial's biostatistician, conduct interim analyses of the data, at intervals of its choosing. The DSMB will meet at least annually, or more frequently if deemed necessary.

15. QUALITY ASSURANCE

15.1 Training

15.1.1 Clinical staff

All clinical personnel (EMS and hospital-based) undergo initial and continuing training in XSTAT[®] application, which reviews indications, methods of deployment, and removal of the sponges. The training also covers the design and objectives of the trial, and data collection procedures.

15.1.2 Research staff

A Standard Operating Procedure Manual (SOPM) developed by the UAB research team provides standard definitions of all study variables (i.e., data elements) and describes all data collection and data entry procedures in detail. Copies of the SOPM will be distributed to all sites to be used in training each site's research team and will be available on the study website through UAB CIS.

Initial training for research assistants and study coordinators is conducted on site. Training includes completing the case report forms, obtaining the laboratory data, and other procedures described in the SPOM. Training of other study staff is the responsibility of trial site coordinators. Training activities will be monitored by the clinical and/or data monitoring team through records of training sessions submitted.

Awareness of the trial protocol in the ED and OR among all staff members is important. Sites will be responsible for orientation and education of all ED personnel on the study to ensure that those designated to collect data are notified of eligible patients upon arrival. Sites may wish to take advantage of staff meetings and in-services to inform and educate the ED staff. Also, the support and collaboration of hospital administrators and physicians can facilitate recruitment and data collection in the ED and OR. The additional tasks required of a research protocol may be taxing in a busy ED setting and, without a show of support from management, procedures outside patient treatment may be inconsistent. The trial sites are responsible for establishing and maintaining coalitions with physicians and hospital administrators to ensure they become stakeholders and receive recognition for their part in the trial.

15.2 Study Monitors

The study monitors will report to UAB. Monitors will be trained in trial procedures, trained to identify source documentation, to assess regulatory compliance, to review source documents for agreement with study records, to identify possible unreported adverse events, and to look for protocol violations. Sites will be visited periodically to assess data quality, review training logs, and monitor study enrollment.

16. PROJECT TIMELINE

16.1 Summary/Gantt Chart

	YEAF	R 1										
	PLANN	IING AN	D PREPA	RATION	PHASE							
	2018			2019								
	Oct	Nov	Dec	Jan	Feb	Mar	Apr	May	Jun	Jul	Aug	Sep
Finalize RevMedx Contract												
Execute CTA with Sites												
Develop Protocol												
Develop Randomization Mechanism												
Develop & test database												
Conduct community consultation & public disclosure												
Obtain HARPO approval												
Obtain IRB approval												
Investigator's Meeting (kick-off meeting)												
Train study personnel												
Site 1 set-up (UAB)												
Site 1 Enrollment Begins (UAB)												
Site 2 set-up (USC)												
Site 2 Enrollment Begins (USC)												
Site 3 set-up (Vandy)												
Site 3 Enrollment Begins (Vandy)							1					
	YEAF	2										
	EXECU	TION PH	IASE									
				2020	2020							
	Oct	Nov	Dec	Jan	Feb	Mar	Apr	Mav	Jun	Jul	Aug	Sep
Enrollment								1				
	YFAR	2										
	EXECU		ASE (co	nt'd)								
	LALCO			2021								
	Oct	Nov	Dec	lan	Feb	Mar	Anr	May	lun	lul	Aug	Sen
Enrollment	000	1101	Dee	Jun	105	IVIGI	дрі	lividiy	Jun	Jui	Aug	Jep
	VEAD	Л										
	TEAF	4										
	EXECUTION PHASE (con							AN	alysis I	PHASE		
	-	h.		2022	I				1	1		6
E sulla s	Oct	Nov	Dec	Jan	Feb	Mar	Apr	May	Jun	Jul	Aug	Sep
Enrollment												
Analysis	_		+		+					+		
Report/Publication												

16.2 Detailed description/Milestones

16.2.1 Year 1: Planning Phase

Task & Timeline	Notes
Develop and document	We will formalize a contractual agreement between
industry partnerships	UAB and $RevMedx^{TM},$ Inc., to include at a minimum,
necessary for conduct of the	intellectual property rights, and data ownership.
clinical trial (Months 0-3)	

Liaison with additional sites (Months 3-6)	Liaise with two additional trauma centers/EMS providers willing to participate in the trial.
Develop protocol, case report forms, and study database (Months 0-6)	We will develop and finalize the clinical trial protocol including a manual of procedures. We will test and finalize case report forms (CRF) for the study. (Sample data collection form in Appendix 2)
Obtain HRPO approval (Months 0-12)	All US Army Medical Research and Materiel Command (USAMRMC) supported research involving humans, human data, human specimens, or cadavers must be reviewed for compliance with Federal and Department of Defense (DoD) human subjects protection requirements and approved by the Office of Research Protections (ORP). The ORP has two human subjects protection review and compliance oversight offices, the Human Research Protections Office (HRPO) and the Clinical Investigations Regulatory Office (CIRO). Our research team has considerable experience obtaining HRPO approval.
Obtain IRB approval (Months 4-9)	Once the protocol is finalized, we will obtain appropriate Institutional Review Board (IRB) approvals.
Conduct Exception From Informed Consent Community Consultation and Public Disclosure Activities (Month 6- 12)	The study will be carried out under federal Exception from Informed Consent (EFIC) regulations. We will conduct all required EFIC community consultation and public disclosure activities.

Training (Months 11-12)Once the protocol is approved by HRPO and the
UAB IRB, we will coordinate prehospital protocol
training. The study team will provide training for all
prehospital care providers, and additional training for
trauma surgeons for the removal of XSTAT® devices.

16.2.2 Year 2/3: Trial Execution Phase

Task & Timeline	Notes
-----------------	-------

Enrollment (Months 13-36) Subject recruitment

16.2.3 Year 3/4: Data Analysis Phase

Task & Timeline	Notes
Data Analysis (Months 25-42)	While data analysis will be ongoing throughout the
	trial, detailed final analyses will be commenced
	during the last year of trial enrollment. We will require
	6 months after trial completion to complete final data
	cleaning and analysis.

18. APPENDICES

Appendix 1: Sample tracking label

The tracking labels are found inside the study packs. They are printed on stiff, waterproof card, are hole-punched, and be supplied with a tie. The label should be completed as directed, and then attached to the patient's wrist or ankle. Labels are specific to trial sites.

PhoXSTAT	Prehospital XSTAT Trial	Kit Number:	
FIRST WOUND TR	EATED	SECOND WOUND	TREATED (IF APPLICABLE)
R	How many devices used on this wound? Only one XSTAT used on this wound Both XSTATs used on this wound	2	How many devices used on this wound?
	Ease of insertion of device into wound: Unable to insert Reasonably easy to use Easily inserted		Ease of insertion of device into wound: Unable to insert Reasonably easy to use Easily inserted
	Ease of deployment of sponges: Unable to deploy sponges Reasonably easy to deploy sponges Easily deployed		Ease of deployment of sponges: Unable to deploy sponges Reasonably easy to deploy sponges Easily deployed
Mark Location	Time device used:	Mark Location	Time device used:
Date:		Vehicle ID:	

Appendix 2: Data Dictionary Codebook

The University of Alabama Ophthalmology Services Foundation

PhoXSTAT

🛄 Codebook 🔻

📖 Data Dictionary Codebook

04/19/2019 1:29pm

r

	 Conapse all instruments 			
	Variable / Field Name	Field Label Field Note	Field Attributes (Field Type, Validation, Choices, Calculations, etc.)	
Instr	strument: Form 5: Randomized to XSTAT (form_5_randomized_to_vstat)			
1	kit_number	Kit label #	text, Identifier	
2	vehicle_id	Vehicle ID #	text	
3	header_f6		descriptive	
4	num_wounds	Section Header: Describe the wounds treated with XSTAT:	radio	
	Show the field ONLY if: [vehicle_id] <> ""	How many wounds were treated with XSTAT?	1 1 2 2	
5	wound_1_loc	Where was the anatomical location of wound #1?	radio	
	Show the field ONLY if: [num_wounds] = '1' or [num_ wounds] = '2'		1 Axilla 2 Groin	
6	wound_1_side	On which side of the body was the wound #1?	radio	
	Show the field ONLY if:		1 Left	
	[num_wounds] = '1' or [num_ wounds] = '2'		2 Right	
7	wound_1_orientation	What was the anatomical orientation of wound #1 (Choose all	checkbox	
	Show the field ONLY if:	that apply)?	1 wound_1_orientation1 Anterior	
	[num_wounds] = '1' or [num_		2 wound_1_orientation2 Posterior	
	wounds] = '2'		3 wound_1_orientation3 Medial	
			4 wound_1_orientation4 Lateral	
8	wound_2_loc	Where was the anatomical location of wound #2?	radio	
	Show the field ONLY if:		1 Axilla	
	[num_wounds] = '2'		2 Groin	
9	wound_2_side	On which side of the body was wound #2?	radio	
	Show the field ONLY if:		1 Left	
	[num_wounds] = '2'		2 Right	
10	wound_2_orientation	What was the anatomical orientation of wound #2 (Choose all	checkbox	
	Show the field ONLY if:	that apply)?	1 wound_2_orientation1 Anterior	
	[num_wounds] = '2'		2 wound_2_orientation2 Posterior	
			3 wound_2_orientation3 Medial	
			4 wound_2_orientation4 Lateral	
11	kit_opened_yn	Section Header: Describe the use of the study protocol:	yesno, Required	
	Show the field ONLY if:	Was kit opened?	1 Yes	
	[num_wounds] = '1' or [num_ wounds] = '2'		0 No	
12	randomized_yn	Was the patient randomized to treatment with XSTAT syringe?	yesno, Required	
	Show the field ONLY if:		1 Yes	
	[kit_opened_yn] = '1'		0 No	

13	xstat_attempted	Was treatment with XSTAT attempted?	yesno, Required		
	Show the field ONLY if: [randomized_yn] = '1'		1 Yes 0 No		
14	violation_reason	Please state reason(s) for protocol violation	notes		
	Show the field ONLY if: [xstat_attempted] = '0' and [r andomized_yn] = '1'				

			0	No	
49	incl_jctl_injury	Penetrating junctional injury (groin or axilla)	rad	lio (Matrix)	
			1	Yes	
			0	No	
50	excl_prisoner	Section Header: Exclusion Criteria Present: To be eligible, all questions must be answered "No"	rad	lio (Matrix)	
		Prisoner, defined as those directly admitted from a correctional facility	0	No	
51	excl_age	Children under the age of 18 years or under 50kg if age	rad	lio (Matrix)	
		unknown	1	Yes	
			0	No	
52	excl_pregnancy	Known pregnancy	rad	lio (Matrix)	
			1	Yes	
1			0	No	

84	inj_named_vein_1 Show the field ONLY if: ([surg_proc_wound(1)] = '1' or ([num_wounds] = '1' and [ope ration_junction_site] = '1')) an d [current-instance] = 1	Injury to named veln?	radio (Matrix) 1 Yes 0 No
85	inj_unnamed_vessel_1 Show the field ONLY if: ([surg_proc_wound(1)] = '1' or ([num_wounds] = '1' and [ope ration_junction_site] = '1')) an d [current-instance] = 1	Injury to un-named vessel?	radio (Matrix) 1 Yes 0 No
86	inj_tissue_bleed_1 Show the field ONLY If: ([surg_proc_wound(1)] = '1' or ([num_wounds] = '1' and [ope ration_junction_site] = '1')) an d [current-instance] = 1	Tissue bleeding?	radio (Matrix) 1 Yes 0 No
87	inj_pleural_violation_1 Show the field ONLY if: ([wound_1_loc] = '1' and ([sur g_proc_wound(1]] = '1' or ([nu m_wounds] = '1' and [operati on_junction_site] = '1'))) and [current-instance] = 1	Pleural violation?	radio (Matrix) 1 Yes 0 No
88	inj_peritoneal_violation_1 Show the field ONLY if: ([wound_1_loc] = '2' and ([sur g_proc_wound(1)] = '1' or ([nu m_wounds] = '1' and [operati on_junction_site] = '1'])) and [current-instance] = 1	Peritoneal violation?	radio (Matrix) 1 Yes 0 No
89	op_arterial_ligation_1 Show the field ONLY if: [surg_proc_wound(1)] = '1' or [(num_wounds] = '1' and [ope ration_junction_site] = '1')	Section Header: Please describe the operative treatment on the wound to the [wound_tside]. [wound_t_orientation] [wound_t_loc]: Ligation of arterial injury	radio (Matrix) 1 Yes 0 No
90	op_venous_ligation_1 Show the field ONLY if: [surg_proc_wound(1)] = '1' or [num_wounds] = '1' and [ope ration_junction_site] = '1')	Ligation of venous injury	radio (Matrix) 1 Yes 0 No
91	op_arterial_repair_1 Show the field ONLY if: [surg_proc_wound(1)] = '1' or ([num_wounds] = '1' and [ope ration_junction_site] = '1')	Patch angioplasty, interposition grafting, or direct repair of arterial injury	radio (Matrix) 1 Yes 0 No
92	op_venous_repair_1 Show the field ONLY if: [surg_proc_wound(1)] = '1' or ([num_wounds] = '1' and [ope ration_junction_site] = '1')	Patch angioplasty, interposition grafting, or direct repair of venous injury	radio (Matrix) 1 Yes 0 No
93	op_other_details Show the field ONLY if: [surg_proc_wound(1)] = '1' or [[num_wounds] = '1' and [ope ration_junction_site] = '1')	Other operative treatment/additional details:	notes

94	sponges_removed_dt_tm_1 Show the field ONLY If: [randomized_ym] = '1' and [xst _proc_wound(1)] = '1' or ([nu m_wounds] = '1' and [operati on_junction_site] = '1') and [x stat_used_wound_1] = '1'	Section Header: Please describe the experience removing the XSMT sponges from the wound to the (wound, I_side), (wound, I_orientation) (wound, I_olc): What was the date and time at which the sponges were finally removed (or when decision was made that they could not be removed? (M-D-Y H:M)	text (datetime_mdy)	
95	ease_sponge_remove_1 Show the field ONLY If: [randomized_ym] = '1' and [xst a_tatempted] = '1' and [Surg _proc_wound(1)] = '1' or ([nu m_wounds] = '1' and [operati on_junction_site] = '1') and [x stat_used_wound_1] = '1'	Please describe the ease of sponge removal	radio 1 Failed to remove all sponges 2 Reasonably easy to remove all sponges 3 Sponges easily removed	
96	time_sponge_removal_1 Show the field ONLY if: [randomized_ym] = '1' and [xst _tatempted] = '1' and [surg _proc_wound(1)] = '1' or ([nu m_wounds] = '1' and [operati on_junction_site] = '1') and [x stat_used_wound_1] = '1'	Please estimate the time required to remove the sponges	radio 1 31 minutes or longer 2 Between 5 and 30 minutes 3 Less than 5 minutes	
97	Imaging_sponge_removal_1 Show the field ONLY If: [randomized_yn] = '1' and [xst at_attempted] = '1' and [surg _proc_wound(1)] = '1' or ([nu m_wounds] = '1' and [operation on_junction_site] = '1']) and [x stat_used_wound_1] = '1'	Please describe what intraoperative imaging was used to ensure removal of the sponges	radio 1 Imaging not used due to patient's condition 2 Imaging not used, as not available 3 Imaging not used, as deemed unnecessary 4 Imaging used	
98	Imaging_outcome_1 Show the field ONLY if: [randomized_yn] = '1' and [ixagi ng_sponge_removal_1] = '4' and ([surg_proc_wound(1])] = '1' or ([num_wounds] = '1' an d [operation_junction_site] = '1') and [xstat_used_wound_ 1] = '1'	Describe the outcome	radio 1 Additional sponges were seen on imaging 2 No additional sponges were seen on imaging	
99	xstat_satisfaction_1 Show the field ONLY if: [randomized_ym] = '1' and [xst at_attempted] = '1' and (surg _proc_wound(1)] = '1' or ([nu m_wounds] = '1' and [operati on_junction_site] = '1'] and [x stat_used_wound_1] = '1'	Please describe your overall satisfaction with the XSTAT device	radio 1 Dissatisfied 2 Neither satisfied nor dissatisfied 3 Satisfied	
100	inj_named_artery_2 Show the field ONLY if: [surg_proc_wound(2)] = '1'	Section Header: Please describe the findings for the wound to the [wound_2_side], [wound_2_orientation] [wound_2_loc]: Injury to named artery?	radio (Matrix) 1 Yes 0 No	
101	inj_named_vein_2 Show the field ONLY if: [surg_proc_wound(2)] = '1'	Injury to named vein?	radio (Matrix) 1 Yes 0 No	
102	inj_unnamed_vessel_2 Show the field ONLY if: [surg_proc_wound(2)] = '1'	Injury to un-named vessel?	radio (Matrix) 1 Yes 0 No	

103	inj_tissue_bleed_2 Show the field ONLY if: [surg_proc_wound(2)] = '1'	Tissue bleeding?	radio (Matrix) 1 Yes 0 No
104	inj_pleural_violation_2 Show the field ONLY if: [surg_proc_wound(2)] = '1' an d [wound,2_loc] = '1'	Pleural violation?	radio (Matrix) 1 Yes 0 No
105	inj_preitoneal_violation_2 Show the field ONLY if: [surg_proc_wound(2)] = '1' an d [wound_2_loc] = '2'	Peritoneal violation?	radio (Matrix) 1 Yes 0 No
106	op_arterial_ligation_2 Show the field ONLY If: [surg_proc_wound(2)] = '1'	Section Header: Please describe the operative treatment on the wound to the [wound_2_side], [wound_2_orientation] [wound_2_loc]: Ligation of arterial injury	radio (Matrix) 1 Yes 0 No
107	op_venous_ligation_2 Show the field ONLY if: [surg_proc_wound(2)] = '1'	Ligation of venous injury	radio (Matrix) 1 Yes 0 No
108	op_arterial_repair_2 Show the field ONLY if: [surg_proc_wound(2)] = '1'	Patch angioplasty, interposition, grafting, or direct repair of arterial injury	radio (Matrix) 1 Yes 0 No
109	op_venous_repair_2 Show the field ONLY if: [surg_proc_wound(2)] = '1'	Patch angioplasty, interposition, grafting, or direct repair of venous injury	radio (Matrix) 1 Yes 0 No
110	sponges_removed_dt_tm_2 Show the field ONLY if: [randomized_yn] = '1' and [xst at_attempted] = '1' and [suta proc_wound(2]] = '1' and [xsta t_used_wound_2] = '1'	Section Header: Please describe the experience removing the XSIAT sponges from the wound to the [wound,2,ide], [wound,2, orientation] [wound,2,loc]: What was the date and time at which the sponges were finally removed (or when decision was made that they could not be removed? (M-D-Y H:M)	text (datetime_mdy)
111	ease_sponge_remove_2 Show the field ONLY if: [randomized_yn] = '1' and [xst at_attempted] = '1' and [surg_ proc_wound[2]] = '1' and [xsta t_used_wound_2] = '1'	Please describe the ease of sponge removal	radio 1 Failed to remove all sponges 2 Reasonably easy to remove all sponges 3 Sponges easily removed
112	time_sponge_removal_2 Show the field ONLY if: [randomized_yn] = '1' and [xst at_attempted] = '1' and [surg_ proc_wound[2]] = '1' and [xsta t_used_wound_2] = '1'	Please estimate the time required to remove the sponges	radio 1 31 minutes or longer 2 Between 5 and 30 minutes 3 Less than 5 minutes
113	imaging_sponge_removal_2 Show the field ONLY if: [randomized_yn] = '1' and [xst at_attempted] = '1' and [surg_ proc_wound(2]] = '1' and [xsta t_used_wound_2] = '1'	Please describe what intraoperative imaging was used to ensure removal of the sponges	radio 1 Imaging not used due to patient's condition 2 Imaging not used, as not available 3 Imaging not used, as deemed unnecessary 4 Imaging used
114	Imaging_outcome_2 Show the field ONLY if: [randomized_yn] = '1' and [sst at_attempted] = '1' and [srt proc_wound[2] = '1' and [ima ging_sponge_removal_2] = '4' and [ixstat_used_wound_2] = '1'	Describe the outcome	radio 1 Additional sponges were seen on imaging 2 No additional sponges were seen on imaging

115	xstat_satisfaction_2 Show the field ONLY if:	Please describe your overall satisfaction with the XSTAT device	radio 1 Dissatisfied
	[randomized_yn] = '1' and [xst at attempted] = '1' and fourg		2 Neither satisfied nor dissatisfied
	proc_wound(2)] = '1' and [xsta t_used_wound_2] = '1'		3 Satisfied
116	form_7_operative_treatment_	Section Header: Form Status	dropdown
	complete	Complete?	0 Incomplete
			1 Unverified
			2 Complete
Instr	rument: Form 8: Blood/Blo	od Product Transfusion Record (form_8_bloodblood_pro	duct_transfusion_record)
117	header_f8		descriptive
118	red_cell_units	Red cell concentrate (units)	text (integer) Field Annotation: @DEFAULT="0"
119	plasma_units	Plasma (units)	text (integer) Field Annotation: @DEFAULT="0"
120	platelet_units	Platelets (units)	text (integer) Field Annotation: @DEFAULT="0"
121	cryo_units	Cryoprecipitate (units)	text (integer) Field Annotation: @DEFAULT="0"
122	whole_blood_units	Whole blood (units)	text (integer) Field Annotation: @DEFAULT="0"
123	form_8_bloodblood_product_	Section Header: Form Status	dropdown
	transfusion_record_complete	Complete?	0 Incomplete
			1 Unverified
			2 Complete
Instr	rument: Form 9: Procoagul	ant medication (form_9_procoagulant_medication)	A Collapse
124	header_f9		descriptive
125	txa_mg	Tranexamic acid (mg)	text (number) Field Annotation: @DEFAULT="0"
126	fibrinogen_mg	Fibrinogen concentrate (mg)	text (number) Field Annotation: @DEFAULT="0"
127	octaplex_mg	Octaplex (mg)	text (number) Field Annotation: @DEFAULT="0"
128	prothrombin_complex	Prothrombin complex concentrate	text (number) Field Annotation: @DEFAULT="0"
129	vitamin_k	Vitamin K	text (number) Field Annotation: @DEFAULT="0"
130	other_procoag_med	Other (specify, including amount)	notes
131	form_9_procoagulant_medica	Section Header: Form Status	dropdown
	tion_complete	Complete?	0 Incomplete
			1 Unverified
	1		
			2 Complete
Instr	rument: Form 10: Admissio	n Blood Work (form_10_admission_blood_work)	2 Complete
Instr 132	rument: Form 10: Admissio	n Blood Work (form_10_admission_blood_work)	2 Complete Collapse descriptive
Instr 132 133	rument: Form 10: Admissio header_f10 blood_gas_source	n Blood Work (form_10_admission_blood_work) Section Header: From blood gas analysis:	2 Complete Collapse descriptive radio
Instr 132 133	rument: Form 10: Admission header_f10 blood_gas_source	n Blood Work (form_10_admission_blood_work) Section Header: From blood gas analysis: Source	2 Complete Collapse descriptive radio 1 Arterial
Instr 132 133	rument: Form 10: Admission header_f10 blood_gas_source	n Blood Work (form_10_admission_blood_work) Section Header: From blood gas analysis: Source	2 Complete Collapse descriptive radio 1 Arterial 2 Venous
Instr 132 133	rument: Form 10: Admissio header_f10 blood_gas_source	n Blood Work (form_10_admission_blood_work) Section Header: From blood gas analysis: Source	2 Complete A Collapse
Instr 132 133 134	rument: Form 10: Admissio header_f10 blood_gas_source lactate	n Blood Work (form_10_admission_blood_work) Section Header: From blood gas analysis: Source Lactate (mmol/L)	2 Complete Collapse descriptive radio 1 Arterial 2 Venous text (number)
Instr 132 133 134 135	rument: Form 10: Admissio header_f10 blood_gas_source lactate basedef	n Blood Work (form_10_admission_blood_work) Section Header: From blood gas analysis: Source Lactate (mmol/L) Base deficit (mmol/L)	2 Complete Collapse descriptive radio 1 Arterial 2 Venous text (number) text (number)

137	hct	Hematocrit (%)	text (number, Min: 0, Max: 100)
138	platelet_count	Platelet count	text (integer)
139	pt	Prothrombin time (s)	text (number)
140	inr	International Normalized Ratio	text (number)
141	aptt	Activated Partial Thromboplastin Time (s)	text (number)
142	teg_r	Section Header: Thromboelastography: R (mins)	text (integer)
143	teg_k	K (mins)	text (integer)
144	teg_alpha_angle	Alpha angle (degrees)	text (number)
145	teg_ma	MA (mm)	text (number)
146	teg_la30	LY30 (%)	text (number, Min: 0, Max: 100)
147	form_10_admission_blood_w	Section Header: Form Status	dropdown
	ork_complete	Complete?	0 Incomplete
			1 Unverified
			2 Complete
Inch	ument: Form 11: Outcome	e /form 11 outromes)	▲ Collarse
1150	based of the	(init_fi_outcomes)	decederity:
148	header_m	la hara Canadia Canad	descriptive
149	injury_iss	Injury Severity Score	text (integer, Min: 1, Max: 75)
150	patient_outcome	Patient	1 Discharmed from acute care
			2 Died
			2 Died
151	dc_date	Discharge date (M-D-Y)	text (date_mdy)
	Show the field ONLY if: [patient_outcome] = '1'		
152	death_date	Date of death (M-D-Y)	text (date_mdy)
	Show the field ONLY if: [patient_outcome] = '2'		
153	icu_ever	Ever in ICU?	yesno
	Show the field ONLY if:		1 Yes
	[patient_outcome] = '1' or [pa tient_outcome] = '2'		0 No
154	icu davs	Days spent in the ICU	text (number)
	Show the field ONLY if:		,
	[icu_ever] = '1'		
155	place_of_death	Where did the patient die?	radio
	Show the field ONLY if:		1 Prehospital (prior to arrival in the ED)
	[patient_outcome] = '2'		2 Emergency Department
			3 Operating Room
			4 Intensive Care Unit
			5 Floor
			6 Palliative Care Unit
156	form_11_outcomes_complete	Section Header: Form Status	dropdown
		Complete?	0 Incomplete
			1 Unverified
			2 Complete
Instr	rument: Form 12: Adverse	Events/Effect Recording Form (form_12_adverse_events	effect_recording_form)
157	header_f12		descriptive
158	event_code	Event/effect code (Choose from list above; leave blank if not	text (integer, Min: 1, Max: 19)
		listed)	

159	event_desc	Description of event	notes					
160	event_start_date	Start date (M-D-Y)	text (date_mdy)					
161	event_end_date	End date (M-D-Y), leave blank if ongoing	text (date_mdy)					
162	event_xstat_related	Relationship to use of XSTAT device?	radio, Required 1 Related ("effect") 2 Unrelated("event")					
163	event_serious	Serious adverse event/device effect?	radio, Required 1 Yes ("serious") 0 No ("not serious")					
164	event_anticipated	Anticipated?	radio, Required 1 Yes ("anticipated") 0 No ("unanticipated")					
165	form_12_adverse_eventseffec t_recording_form_complete	Section Header: Form Status Complete?	dropdown 0 Incomplete 1 Unverified 2 Complete					
Inst	Instrument: Form 13: Subject/LAR Consent (form_13_subjectlar_consent)							
166	header_f13		descriptive					
167	died_before_lar	Please check this box if the patient died before contact was made with the LAR	checkbox 1 died_before_lar1					
168	contact_date_time	Contact Date and Time (M-D-Y H:M)	text (datetime_mdy)					
169	contact_purpose	Purpose of contact	radio 1 Contacting LAR for consent 2 Contacting participant for consent					
170	contact_type	Type of contact	radio 1 Phone 2 In person 3 Other					
171	contact_type_other Show the field ONLY if: [contact_type] = '3'	Specify	text					
172	contact_outcome	Outcome	radio 1 Made contact, consent given 2 Made contact, consent not given 3 No reply, did not make contact 4 Note additional information on Form 14					
173	form_13_subjectlar_consent_ complete	Section Header: Form Status Complete?	dropdown 0 Incomplete 1 Unverified 2 Complete					
Instrument: Form 14: Additional Information (form_14_additional_information)								
174	header_f14		descriptive					
175	form_no	Form Number	text (integer, Min: 1, Max: 13)					
176	additional_details	Additional details	notes					

177	form_14_additional_informati on_complete	Section Header: Form Status Complete?	dropdown 0 Incomplete	
			1	Unverified
			2	Complete

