1.2 Eligible population

Patients aged 15 years and over, or with an estimated body weight of 50kg or more; who have suffered a penetrating junctional injury (femoral or axillary) with visible bleeding; who a suffering from class 3 or 4 hemorrhagic shock; and who will be taken directly to a level I trauma center participating in the PhoXSTAT trial.

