6.2.1 Inclusion criteria

- a) Age \geq 15 years or estimated body weight \geq 50 kg.
- b) Penetrating junctional injury (femoral or axillary), with
 - i. visible bleeding
 - ii. too proximal to be controlled with a tourniquet
- c) Class 3 or 4 hemorrhagic shock
- d) Patient will be taken to participating level I trauma center, directly from the scene

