6.2.2 Exclusion criteria

- a) Prisoners, children <15 years old, known pregnant patients.
- b) Patients receiving chest compressions (prior to XSTAT[®] use).
- c) Patients with an opt-out bracelet.

Adolescents will be included because children aged 15 and over are typically transported to, and treated, in adult trauma centers. Only children below this age are taken to specialist pediatric trauma centers (when available).

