8.2 Case Report Form

Data is initially collected using paper Case Report Forms (CRFs, appendix 2), and then transcribed into an electronic database. The electronic CRF uses the Research Electronic Data Capture (REDCap) system, a secure research database developed by NIH. Data logic checks are used to minimize data entry errors. Data audits are performed on a randomly selected 20% of enrolled subjects. When data are complete, and all suspect entries addressed, the database will be "locked" and exported to STATA or SAS for analysis.

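### The eligibility form in Appendix 2 excludes patients under 18, while sections 1.2 and 6.2 set the age limit at 15

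*Protocol*

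**What the plan says.** Section 1.2 of the protocol describes the population as "Patients aged 15 years and over, or with an estimated body weight of 50kg or more". Section 6.2.1(a) offers the same two routes, an age of at least "15 years or estimated body weight" of at least 50 kg. Section 6.2.2(a) excludes "Prisoners, children <15 years old, known pregnant patients", and the text below it gives a reason: "Adolescents will be included because children aged 15 and over are typically transported to, and treated, in adult trauma centers". Only 6.2.2 says in words that adolescents are included.

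In Appendix 2, Form 2, field 51 (excl_age) lists as an exclusion "Children under the age of 18 years or under 50kg if age"; the last word of the label, unknown, falls on the next line. The header of that block requires a no to every exclusion item for the patient to be eligible. Form 1 records year of birth (field 38). When that is unknown, it records an estimated age in bands that begin with under 15, 15-19 and 20-34 (field 40).

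On the standing of the appendix, section 8.2 says "Data is initially collected using paper Case Report Forms (CRFs, appendix 2), and then transcribed into an electronic database". Section 16.2.1 says "We will test and finalize case report forms (CRF) for the study. (Sample data collection form in Appendix 2".

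**The concern.** The protocol contains two lower age limits. The limit of 15 looks deliberate, because 6.2.2 gives a reason for it. The limit of 18 stands on the form whose purpose is to verify eligibility. Form 1 breaks its age bands at 15 and not at 18, so the appendix is also at odds with itself.

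This is a feasibility trial, and section 10.1 promises the number of patients meeting the inclusion criteria alongside the number enrolled and randomized. If the first number were taken from Form 2, it would rest on a different rule from the one in 6.2. Monitors who check study records and look for violations (15.2) could likewise query an enrolment that 6.2 allows.

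**Working it through.** The protocol gives no figure to reproduce. The check sets the two rules side by side.

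**Inputs**
- Section 6.2.1(a): in if age is at least 15, or estimated weight is at least 50 kg.
- Section 6.2.2(a): out if age is under 15.
- Form 2, field 51: out if age is under 18, or if age is unknown and weight is under 50 kg.
- Form 1, fields 38 to 40: birth year, a tick for birth year unknown, and the estimated-age bands.

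The label of the matching inclusion item (field 47, incl_age) is garbled in the available text and is not used.

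**Step 1: known age.** With 6.2.1 and 6.2.2 applied together, weight cannot bring in a patient known to be under 15, so 6.2 reduces to age ≥ 15. Field 51 reduces to age ≥ 18. They differ where 15 ≤ age < 18, which is 18 − 15 = 3 single years (15, 16 and 17), at any weight.

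| Known age, weight | Section 6.2 | Field 51 |
|---|---|---|
| 14, 55 kg | out (meets 6.2.1 by weight, excluded by 6.2.2) | out |
| 16, 45 kg | in | out |
| 16, 60 kg | in | out |
| 20, 45 kg | in | in |

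**Step 2: birth year unknown.** The result depends on whether an estimated age counts as an age, which neither section 6.2 nor the legible part of Form 2 settles.
- If it counts in neither place, both rules turn on 50 kg and agree.
- If it satisfies the age route in 6.2.1 while field 51 treats the age as unknown, a patient estimated at 20-34 and weighing 45 kg is in under 6.2 and out under field 51. Here the weight rule alone reverses the answer.
- If it counts in both places, the conflict at 15 to 17 returns, and field 51 cannot be applied within the 15-19 band.

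**Step 3: can the error be undone from Form 1?** Let d = arrival year − birth year. Age is then d − 1 or d. For a limit of 15, only d = 15 is ambiguous (age 14 or 15). For a limit of 18, only d = 18 is ambiguous (age 17 or 18). Without a birth year, the bands can apply a limit of 15 but not one of 18. Most misrecorded patients could therefore be reclassified.

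**Step 4: which outputs depend on Form 2?** Under 6.3.2 the ambulance crew judges eligibility and opens the pack, so Form 2 does not control entry. Section 10.1 names no source for the count of patients meeting the criteria.

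**Scale.** Section 9 anticipates at most 50 enrolled patients. At that ceiling one misrecorded patient is 1/50 = 2% of those enrolled, and more if fewer enrol. The protocol gives no age distribution, so the number aged 15 to 17 is unknown.

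**The case against.** The strongest reply is that this is one field in a form that 16.2.1 calls a sample, still to be tested and finalized, and that violations are judged against the protocol and not against a sample form. It can be added that 10.1 counts patients who meet inclusion criteria, whereas field 51 is an exclusion item, and that no section says the count comes from Form 2. Most of this stands. It is why the effects on 10.1 and on monitoring are put as conditional, and why the point is minor. It does not remove the contradiction: field 51 is legible, both texts are current, and 8.2 cites the same appendix as the forms in use.

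A reader might go further in four ways that the protocol does not support.
- That adolescents would be kept out of the trial, or that the enrolled count would be wrong. Entry is fixed when the pack is opened in the field.
- That the print stamp "04/19/2019 1:29pm" shows the form was final. A print date does not establish that, and a later version may have changed the limit.
- That the form omits class 3 or 4 shock and visible bleeding, because the visible inclusion items do not include them. Fields 53 to 83 are not shown and may hold them.
- That the two rules always agree when age is unknown, so that the weight wording is harmless. Step 2 of the check gives a counterexample on a natural reading of 6.2.1.

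**Conclusion.** The inconsistency is real and minor. For patients of known age, section 6.2 and field 51 give opposite answers at 15, 16 and 17 and agree at other ages. This takes 6.2.1 and 6.2.2 together, with the exclusion overriding the weight route. For patients of unknown birth year, the different role of weight can also reverse the answer, depending on whether an estimated age counts as an age.

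The number enrolled and randomized does not change, and no effect on usability, safety or the comparison of groups is claimed. The count of eligible patients in 10.1, and any violation review, would depart from 6.2 only to the extent that they use Form 2. The number of patients concerned cannot be stated. The protocol does not settle which limit is intended throughout, and this review does not choose one.

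**What to change.** Before the form is used:

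1. Reconcile the age limit and the role of weight across 1.2, 6.2.1, 6.2.2 and Form 2 (incl_age and excl_age), and state whether an estimated age counts as an age. If the reconciled limit does not fall on a band boundary in field 40 of Form 1, add a break there.
2. Add one line to 10.1 saying that the count of patients meeting the criteria uses the reconciled criteria.

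The cost is a small revision of the paper and electronic forms and one sentence in 10.1. No new data item is needed. If forms have already been completed under the limit of 18, most can be reclassified from birth year, and the few ambiguous records can be listed.
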